4.4.2 Blinding

The Treating Investigator will not be blinded to study treatments.

A Blinded Evaluator, to whom randomization and treatment are concealed, will conduct the blinded assessments. To the extent possible, the same Blinded Evaluator should assess an individual subject throughout the study.

The Blinded Evaluator is not allowed to be present during the injections or to discuss treatments with the Treating Investigator or subjects. All documents with information regarding study products and randomization assignment should be kept in a separate file not available to the Blinded Evaluator.

	
CCI
 

 

 
Title CTN 43BBJ1911 US Jawline, Clinical Investigation Plan

---	--

Safety assessments will be performed by non-blinded personnel as treatment-related AEs are expected to occur during a few days after treatment, thereby revealing which subjects have received the study product.

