10.5 Safety analysis

All AEs will be coded according to MedDRA and summarized by system organ class (SOC), preferred term (PT) and treatment (no treatment, 1st treatment including touch-up if applicable, and 2nd treatment).

A summary of all AEs will be provided, which will include:

- number of subjects with at least one AE and number of events (in total as well as serious AEs)
- number of subjects with at least one related AE and number of events (in total as well as serious AEs)
- number of subjects with at least one unrelated AE and number of events (in total as well as serious AEs)
- number of subjects who did not have an AE

The number of subjects with AEs related to study product or injection procedure as well as the number of events will be summarized by SOC, PT and maximum severity. In addition, for related AEs the number of days to onset and the duration of event will be summarized by SOC and PT using mean, SD, min, max and median. Action taken for related AEs will also be summarized. Serious AEs, and AEs with onset >21 days after most recent treatment will be listed.

Non-related AEs will be summarized by SOC, PT and intensity.

To evaluate consistency of AEs across different subgroups, AEs will also be summarized by subgroups defined as described below.

Safety analysis will be descriptive only.

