2.5.2 Adverse Events (AEs)

All AEs will be summarized relative to treatment session timing using the following categories:

- No Treatment at Baseline: For subjects who receive no treatment at baseline, include AEs before any optional GP0109 treatment at Month 12.
- Initial Treatment with GP0109: Pool AEs for the following (whether optional touch-up treatment received or not):
 - For subjects treated with GP0109 at baseline:
 - include AEs before optional GP0109 re-treatment at Month 12,
 - include AEs through end of study if no re-treatment at Month 12.
 - For subjects who receive no treatment at baseline, include AEs after initial GP0109 treatment at Month 12.
- Re-treatment with GP0109: For subjects treated with GP0109 at baseline, include AEs after optional GP0109 re-treatment at Month 12.

All AEs will be coded according to MedDRA and summarized by System Organ Class (SOC), Preferred Term (PT), and treatment session timing as described above. The number of subjects with at least one event, associated percentage, and number of events will be provided.

For subject counts, a subject will only be counted once per SOC and once per PT in cases where multiple events are reported for a subject within SOC or PT. For event counts, subjects with multiple events in a category will be counted for each event.

The number of subjects with AEs related to study product or study product injection procedure and unrelated AEs, as well as the number of events, will be presented by SOC, PT, and maximum intensity. Action taken for related AEs will also be summarized by SOC and PT using number of events. AEs related to study product or injection procedure with late onset (> 21 days after most recent treatment session) will be listed.

Serious AEs and AEs of special interest (AESIs) will be listed. See Section 8.2.1 of the protocol for a list of visual disturbances considered to be AESIs.

For AEs related to study product or study product injection procedure, the number of days to onset and the duration of event will be summarized by SOC and PT using mean, standard deviation, median, minimum, and maximum. Days to onset of an AE will be derived as the start date minus the date of most recent treatment session. Duration of an AE will be derived as the stop date minus the start date + 1. Missing stop date will not be imputed, and therefore no duration will be calculated in these cases.

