2.6 Interim Analysis

A safety review will occur after all subjects randomized in Stage 1 complete the follow-up visit at 3 months after baseline. The sponsor will submit select baseline and all safety data to the FDA for review and will await the agency's agreement prior to continued enrollment into Stage 2. The tables and listings to be included in this submission will include the following:

- Table for subject disposition and reasons for study discontinuation,
- Table for demographics and baseline characteristics,
- All safety tables for adverse events, subject diary symptoms, treatment administration characteristics, injection volume, jawline mobility, intra-oral exam, pronunciation, jawline sensation, facial nerve function, palpation, and visual function assessments.
- Listings for product complaints and related adverse events with late onset.

In addition, an interim analysis based on 12 months data from baseline is planned for this study to be used for early regulatory submission. This includes data for all subjects (both Stage 1 and Stage 2) up to this timepoint. The study will continue without modification afterwards, i.e., subjects will have no further treatment and will continue follow-up through 24 months after baseline. All data collected up to the interim analysis will be verified and cleaned; however, data may be updated later, if applicable, until final closure of the study database.

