2.8 Changes in the Analysis Planned in the Protocol

Other than the addition of analyses described in SAP Section 2.4.4 CCI here have been no substantial changes from the statistical methods described in the protocol.

	
Title
 
43BBJ1911 - Statistical Analysis Plan - Big Ben Jawline

--	---

3 Reference List

There are no other references beyond those that are included in the protocol.

The Galderma logo features the word 'GALDERMA' in a bold, sans-serif font, with 'EST. 1981' in a smaller font below it.	
Title
 
43BBJ1911 - Statistical Analysis Plan - Big Ben Jawline

---	---

5 Schedule of Events

Procedure	Visit 1a	Visit 1b	Visit 2a ⁴	Visit 2b ⁴	Visit 3	Visit 3a ⁴	Visit 3b ⁴	Visit 3c ⁴	Visit 4	Visit 5	Visit 6	Visit 7	Visit 7a ⁴	Visit 7b ⁴	Visit 7c ⁴	Visit 8	Visit 9	Visit 10	Visit 11
	Visits may be combined if subject meets eligibility criteria		72 hrs after Tx (±24 hrs)	14 days after baseline (+7 days)	1 month ¹⁰ after baseline (+7 days)	72 hrs after optional TU (±24 hrs)	14 days after optional TU (+7 days)	1 month ¹⁰ after optional TU (+7 days)	3 months ¹⁰ after baseline (±7 days)	6 months ¹⁰ after baseline (±7 days)	9 months ¹⁰ after baseline (±7 days)	12 months ¹⁰ after baseline (±7 days)	72 hrs after optional Tx (±24 hrs)	14 days after optional Tx (+7 days)	1 month ¹⁰ after optional Tx (+7 days)	15 months ¹⁰ after baseline (±7 days)	18 months ¹⁰ after baseline (±7 days)	21 months ¹⁰ after baseline (±7 days)	24 months ¹⁰ after baseline (+7 days)
	Screening Day -30 to 1	Baseline/Tx Day 1	TC	Follow-up	Follow-up/Optional TU	TC	Follow-up	Follow-up	Follow-up	Follow-up	Follow-up	Follow-up/Optional Tx/EOS ¹¹	TC	Follow-up	Follow-up	Follow-up	Follow-up	Follow-up	Follow-up/ EOS
Informed Consent	X																		
Med. Hx/prior therapies	X	X ^{1,2}																	
Demographics	X																		
Height/Weight ⁶		X ^{1,6}																	X ⁶
Inclusion/Exclusion Criteria	X	X ^{1,2}			X ^{1,5}							X ^{1,5}							
Urine pregnancy test ³	X	X ^{1,2}			X ^{1,5}							X ^{1,5}							X
Randomization		X																	
Treatment with study product		X ⁹			X ^{5,9}							X ⁵							
Evaluate device deficiencies		X ⁹			X ^{5,9}							X ⁵							
Dispense Subject Diary		X ⁹			X ^{5,9}							X ⁵							
Collect/Review Subject			X ⁷	X	X ⁹	X ⁷	X	X					X ⁷	X	X				
Photography		X ¹		X	X ¹		X	X	X	X	X	X ¹		X	X	X	X	X	X
Concomitant therapies	X	X ²	X	X	X	X	X	X	X	X	X	X	X	X	X	X	X	X	X

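### The SAP limits the late-onset AE listing to events judged related, where Protocol 10.5 sets no causality condition, and SAP 2.8 does not declare the change

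*SAP*

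**What the plan says.** Protocol 10.5 (Safety analysis) states: "Serious AEs, and AEs with onset >21 days after most recent treatment will be listed". Earlier in the same paragraph, the onset and duration summaries are limited explicitly: "for related AEs the number of days to onset and the duration of event will be summarized by SOC and PT".

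SAP 2.5.2 states: "AEs related to study product or injection procedure with late onset (> 21 days after most recent treatment session) will be listed". For onset and duration it says: "For AEs related to study product or study product injection procedure, the number of days to onset and the duration of event will be summarized". It also provides listings of serious AEs and AEs of special interest without a causality condition, and tabulates unrelated AEs by SOC, PT and maximum intensity.

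For the Stage 1 submission, SAP 2.6 itemises tables, including "All safety tables for adverse events, subject diary symptoms, treatment administration characteristics, injection volume, jawline mobility" and others, followed by "Listings for product complaints and related adverse events with late onset".

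SAP 2.1 gives the SAP precedence over the protocol's statistical sections where they differ. SAP 2.8 reports, apart from added analyses in 2.4.4, that "here have been no substantial changes from the statistical methods described in the protocol" (the first letter is lost to a redaction).

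**The concern.** The two documents use the same 21-day cut-off but define different event sets. The protocol's set is every late AE; the SAP's is every late AE that someone has judged related. Because the SAP governs, its set is the one that would be produced.

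Attribution is harder for a delayed event than for one seen in the days after injection. Relatedness is a Yes/No judgement by the investigator (Protocol 8.11.5.2), and on the injecting side "The Treating Investigator will not be blinded to study treatments". A listing without the filter lets a reader examine that judgement; a filtered one takes it as given. The SAP also does not say whether the investigator's or the sponsor's assessment drives the filter.

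This matters most at Stage 1. Protocol 2.4 says that there is no previous clinical experience with GP0109 and gives unforeseen risk as the reason for staging. Protocol 10.9 provides no data monitoring committee, and Stage 2 waits for the FDA's agreement after its review of about 50 subjects.

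**Working it through.** No sample size, power or event count enters this point, so there is no figure to reproduce. The check is a comparison of text.

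**1. Listing scope**

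| Item | Protocol 10.5 | SAP 2.5.2 | SAP 2.6 (Stage 1) |
|---|---|---|---|
| Cut-off | >21 days after most recent treatment | >21 days after most recent session | late onset, not restated |
| Causality condition on the late-onset listing | none | related only | related only |
| Days-to-onset summary | related only | related only | through the AE tables, so related only |

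Only the causality condition on the listing differs. The days-to-onset summary agrees between the documents.

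**2. Is the missing condition in the protocol deliberate?** The paragraph in 10.5 writes the restriction out for the counts by severity, for onset and duration, and for action taken. The listing sentence leaves it out and joins late AEs to serious AEs, which carry no causality condition either. The literal reading is therefore all late AEs.

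**3. Is the change declared?** The readable text of SAP 2.8 names only the added analyses.

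**4. Could a version difference explain it?** The SAP cites protocol v3.0, while the protocol at hand is v4.0. The readable rows of the change summary in Protocol 12.3.2 show no change to 10.5, so a version difference does not visibly account for it.

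**5. Where does a late, non-serious AE rated unrelated appear under the SAP?**

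- In the all-AE table by SOC and PT, and the unrelated-AE table by maximum intensity: yes, without an onset time.
- In the days-to-onset summary: no.
- In the late-onset listing: no.
- In the general subject listings (Protocol 10.1, SAP 2.1.2), which carry the eCRF data: yes, with its start date.
- In the Stage 1 outputs itemised in SAP 2.6: in the AE tables only. Neither of the two listings named there covers it.

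For such an event, then, the itemised Stage 1 outputs give a count but no onset time.

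**6. Does the wider listing need new data?** No. Start date, affected area and causality are eCRF fields (Protocol 8.11.5), and SAP 2.5.2 already defines days to onset as start date minus the date of the most recent session.

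**The case against.** The strongest reply is that Protocol 10.5 can be read more narrowly. The listing sentence closes a paragraph mostly about related AEs, and the next paragraph gives non-related AEs a summary of their own with no listing. On that reading the SAP merely makes the intent explicit. This has some force, but the sentence itself is unqualified and its other half, serious AEs, is plainly not limited to related events. At best the protocol is ambiguous, and the SAP settles the ambiguity without saying so.

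A reader might infer that the restriction hides late events from the FDA. The documents do not support that. SAP 2.6 says that all safety data will be submitted, the AE tables count unrelated events, and the general listings carry start dates. SAP 2.5.2 lists serious AEs and AEs of special interest regardless of cause, and Protocol 8.11.8 has visual disturbances expedited to the FDA whatever their relationship to the product. The protocol itself prescribes no Stage 1 listings. What stands is that the outputs SAP 2.6 itemises do not show the timing.

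A reader might also take the related-only days-to-onset summary as a second departure. It is not one, because the protocol has the same limit.

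On attribution there are safeguards. A Yes to either of two questions, product or procedure, makes an event related, and the sponsor assesses every AE separately. These lower the chance of a wrong unrelated rating; they do not make the rating visible in the late-onset listing.

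Finally, the most recent treatment is undefined for a control subject before any treatment, so a wider listing has no untreated comparator. That is true under both documents' rules and is acceptable for a descriptive listing.

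**Conclusion.** The discrepancy is real and minor. The SAP narrows a listing for which the protocol set no causality condition, repeats the narrowing for Stage 1, and does not declare it in readable text. The effect is confined to that listing: late AEs rated unrelated leave it, and the itemised Stage 1 outputs do not show their onset timing. No endpoint, table count, rate, stopping rule or decision criterion changes, and safety analysis is descriptive throughout. The documents give no expected number of such events, so the effect cannot be put as a count.

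This rests on the literal reading of Protocol 10.5, and on no redacted text, in SAP 2.8 or elsewhere, declaring the restriction.

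**What to change.** In SAP 2.5.2 and in the Stage 1 listings of SAP 2.6, list all AEs with onset more than 21 days after the most recent treatment session, regardless of causality. Show relatedness, affected area and days to onset as columns, and derive days to onset for every listed event, not only for related ones. State whether the relatedness column is the investigator's assessment, the sponsor's, or both. The related-only days-to-onset summary table can stay as it is.

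If the sponsor prefers the narrower listing, SAP 2.8 should declare and justify it; that removes the undeclared change but leaves the Stage 1 timing gap.

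The cost is SAP wording, a small programming change and a longer listing that will include incidental illnesses. Sorting treated-area events first would keep it readable. No new data, visits or subjects are needed.

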3.1 Objectives and endpoints

3.1.1 Primary objective and endpoint

The primary objective of the study is to demonstrate superiority of GP0109 versus no treatment control in jawline definition.

Endpoint:

GALDERMA <small>EST. 1987</small>	Title CTN 43BBJ1911 US Jawline, Clinical Investigation Plan
---	--

- ☐ Responder rate based on the Blinded Evaluators’ live assessment using the GJS, at 3 months after baseline.
- A responder is defined as a subject with at least 1 grade improvement from baseline, on both jawlines concurrently.

- 3.1.3 Safety objectives The safety objectives and endpoints are:
- To evaluate the incidence, intensity, time to onset and duration of adverse events (AEs) collected throughout the study period.
- 

4. Design of the Study

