8.11.5 Recording instructions

When an AE is related to a device deficiency (refer to section 8.12), including technical device malfunction, the AE shall be recorded on the AE form/module in the eCRF and the technical complaint shall be reported separately on the clinical study complaint form provided separately in the Investigator file.

Investigators, or other study site personnel, shall record all AEs in the eCRF, including:

- Event term (recorded in standard medical terminology and avoiding abbreviations)
- Affected area
- Start date (first day with symptoms)
- Stop date (last day with symptoms)
- Intensity (mild, moderate, or severe according to definition in section 8.11.5.1)
- Seriousness (serious or not serious, according to definition in section 8.11.5.2)
- Causal relationship to study product or study product injection procedure (yes or no)
- Action taken (none, medication treatment, non-pharmacological treatment, or other procedures/tests, subject withdrawn)
- Outcome of the AE (ongoing, recovered, recovered with sequelae, death, chronic/stable, not recovered at the end of the study)

The AE form/module in the eCRF must be signed and dated by the Investigator.

	Title CTN 43BBJ1911 US Jawline, Clinical Investigation Plan
---	--

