8.11.11 Follow-up of unresolved events ongoing at termination of the study

All serious as well as non-serious AEs with a causal relationship to the study product or treatment procedure and ongoing at study end, shall be followed up after the subject's participation in the study is over. Such events shall be followed-up after the last study visit until resolved, assessed as chronic or stable, or subject is lost to follow up. Final outcome after the end of the study shall be reported on the AE Follow-up form.

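### AE duration is summarised only for events with a stop date, so unresolved related events drop out and the reported duration is biased short

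*SAP*

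**What the plan says.** Protocol 3.1.3 makes duration part of the safety objective: "To evaluate the incidence, intensity, time to onset and duration of adverse events (AEs) collected throughout the study period".

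SAP 2.5.2 gives the derivation: "Duration of an AE will be derived as the stop date minus the start date + 1". On missing dates it says: "Missing stop date will not be imputed, and therefore no duration will be calculated in these cases". For AEs related to the product or the injection procedure, days to onset and duration "will be summarized by SOC and PT using mean, standard deviation, median, minimum, and maximum". Protocol 10.5 plans the same summary. The readable text of both documents contains no censored-data method for duration and no planned count of unresolved events beside it.

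Protocol 8.11.5 has sites record "Stop date (last day with symptoms") and "Outcome of the AE (ongoing, recovered, recovered with sequelae, death, chronic/stable, not recovered at the end of the study"). The recorded outcome therefore identifies unresolved events, but the duration analysis does not use it.

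Protocol 8.11.11 covers related events still open at study end: "Such events shall be followed-up after the last study visit until resolved, assessed as chronic or stable, or subject is lost to follow up". It adds: "Final outcome after the end of the study shall be reported on the AE Follow-up form". Neither document says whether dates from that form enter the duration analysis.

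SAP 2.6 schedules two outputs before the final one. The first is a Stage 1 safety submission once all Stage 1 subjects have completed Month 3, and it includes all the AE safety tables. The second is a 12-month interim analysis for early regulatory submission.

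**The concern.** An event that still has symptoms has no last day with symptoms. Its duration is not unknown in the ordinary sense. It is right-censored, meaning that it is known to be at least the time elapsed so far. Removing such events and averaging the rest conditions on resolution before the data cut, which favours short durations.

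Persistent events are plausible here. Protocol 2.4 names mass/induration among the most common post-marketing complaints after jawline/chin treatment, and Protocol 8.5 has any unexpected feel on palpation reported as an AE. Daily diaries run for only 28 days per treatment session (SAP 1.4), so longer persistence has to be read from the AE records. A reader of the duration table could conclude that a given event type clears quickly when the table shows only the cases that did clear.

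**Working it through.** The documents state no AE duration and no share of unresolved events, so there is no figure to reproduce. The check asks which way the rule pushes the result, and how far under stated assumptions.

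**Inputs from the documents.** One month is 28 days (Protocol 4.3). The cuts are therefore 3 × 28 = 84 days (Stage 1), 12 × 28 = 336 days (interim) and 24 × 28 = 672 days (final). These apply to events that start at the baseline treatment. Follow-up is shorter for events that start at the 1-month touch-up (84 − 28 = 56 days at Month 3). It is longer for Stage 1 subjects who enrolled early.

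**Assumed inputs.** The true mean duration m, the share f unresolved at the cut, and a 10-day mean among resolved events. Each of m and f is shown over a range.

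**A. Exponential durations with onset at treatment.** With cut C, the share still open is q = exp(−C/m). The mean among resolved events is m − C·q/(1 − q). For C = 84 and m = 30, q = exp(−2.8) = 0.0608, and the mean is 30 − 84 × 0.0608/0.9392 = 24.6 days.

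| Cut (days) | True mean | Open at cut | Reported mean | Bias |
|---|---|---|---|---|
| 84 | 14 | 0.2% | 13.8 | −1.5% |
| 84 | 30 | 6.1% | 24.6 | −18% |
| 84 | 60 | 24.7% | 32.5 | −46% |
| 84 | 120 | 49.7% | 37.1 | −69% |
| 336 | 60 | 0.4% | 58.8 | −2% |
| 336 | 120 | 6.1% | 98.2 | −18% |
| 336 | 240 | 24.7% | 130.0 | −46% |
| 672 | 120 | 0.4% | 117.5 | −2% |
| 672 | 240 | 6.1% | 196.5 | −18% |

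The bias is never upward in this model. For a given true mean it is largest at the earliest cut. The median moves less than the mean but is not immune. At 84 days a true median of 20.8 (m = 30) is reported as 19.0, and one of 41.6 (m = 60) as 28.4.

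**B. A small share of persistent events.** A share f is still open at C, and the rest have a mean of 10 days. The plan reports 10 days. The true mean is at least (1 − f) × 10 + f × C. For f = 1% and C = 84, that is 9.9 + 0.84 = 10.7.

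| f | C = 84 | C = 336 | C = 672 |
|---|---|---|---|
| 1% | 10.7 | 13.3 | 16.6 |
| 2% | 11.5 | 16.5 | 23.2 |
| 5% | 13.7 | 26.3 | 43.1 |
| 10% | 17.4 | 42.6 | 76.2 |

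These are lower bounds because open events continue. Model B holds f fixed, so its larger gaps at later cuts come only from the larger C. It does not rank the outputs by bias.

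**The case against.** The strongest reply is that this is a descriptive table with an openly stated exclusion, and that the missing information appears elsewhere:

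- SAP 2.1.2 lists all eCRF data by subject, and SAEs, AESIs and late-onset related AEs have their own listings.
- Palpation is done at every physical visit and summarised (SAP 2.5.4), so persistent lumps can be seen outside the duration table.
- Subject counts normally accompany quantitative summaries, so a shortfall would be partly visible.
- Related events are followed after study exit, and data may be updated until the database finally closes.
- Protocol 6.5.3 expects common injection reactions to clear within two weeks, where the bias is negligible.
- Medians may move little. If 10% of events stay open and resolved durations are exponential with mean 10, the Kaplan-Meier median solves 0.1 + 0.9·exp(−t/10) = 0.5. That gives t = 8.1 days, against 10 × ln 2 = 6.9 for resolved events only.

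Most of this stands as a limit on importance. None of it corrects the duration summary. Follow-up after a cut cannot help the Month 3 or 12-month output, and it gives no stop date to events that end as chronic/stable or lost to follow-up. SAP 2.5.3, on expected post-treatment events, is redacted and is not judged here.

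A reader might also infer more than the documents support:

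- **That every omitted event is among the longest.** The rule covers any missing stop date. It also drops resolved events with an unrecorded date and recent events still open at a cut.
- **That the reported maximum must be wrong.** It is the correct maximum of resolved durations, and a long event that resolves does appear. It may be too low as a maximum for all related events.
- **That the 12-month interim is the worst case.** Model A puts the greater relative bias at Month 3 for any given duration.

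**Conclusion.** The point holds for the duration summary of related AEs. The direction follows from the rule itself: leaving out unresolved events biases reported duration short. The size cannot be stated because the documents give no rate of unresolved events. Shares of 5% or 10% open are illustrations, not expectations.

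Under the exponential assumption the bias is at most 1.5% for a two-week mean. It reaches 18% to 46% for true means of 30 to 60 days at the Stage 1 output, and 18% for a true mean of 120 days at the 12-month interim. Incidence, intensity and time to onset are unaffected, and no test depends on this summary. It should still be corrected, because duration is a stated objective and the two early outputs go to, or support submission to, the regulator.

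**What to change.** Amend SAP 2.5.2 as follows:

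1. Beside the duration summary, show by SOC and PT, at each data cut, the number and percentage of related AEs without a stop date. Separate unresolved events from resolved events whose date was not recorded. For unresolved events, give the time elapsed to last contact or cut-off as a lower bound on duration.
2. Label the existing mean, SD, median, minimum and maximum as *resolved events only*.
3. Treat unresolved events as right-censored, and give a Kaplan-Meier median and quartiles for terms with enough events.
4. State that stop dates from the AE Follow-up form are used where available before final database closure.

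Start dates and outcomes are already collected, so no new data are needed. The cost is modest extra programming and independent validation, which is more than a single added column. Estimates for rare terms will be sparse, so items 1 and 2 matter most.
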